2.3 Exploratory Objectives and Endpoints

Type	Objective	Endpoints
[REDACTED]	[REDACTED]	[REDACTED]

Table 3 **Exploratory Objectives and Endpoints**

Type	Objective	Endpoints
[REDACTED]	[REDACTED]	[REDACTED]
[REDACTED]	[REDACTED]	[REDACTED]
[REDACTED]	[REDACTED]	[REDACTED]

3 STUDY DESIGN

3.1 Description of the Study

3.1.1 Overview

This is a randomised, double-blind, placebo-controlled study to evaluate the safety, tolerability, efficacy, and PK profile of MEDI0382 titrated from [REDACTED] up to [REDACTED] and administered once daily by subcutaneous (SC) injection over 32 days in subjects with T2DM and renal impairment ($eGFR \geq 30$ and < 60 mL/min/1.73 m²). The study has a 14-day run-in period of diet and exercise and continuous glucose monitoring (CGM), a 32-day treatment period, and a 28-day follow-up. Diet and exercise guidance will be according to local practices. It is planned to randomise approximately 40 subjects across multiple study sites. Subjects will be consented, screened for suitability, and randomised within 40 days of screening, if eligible.

Throughout the study, subjects will have the choice to either travel to the clinic for visits or stay overnight locally whenever consecutive daily visits are required. Subjects will be expected to fast for at least 8 hours overnight prior to Visit 3 (Day -5), Visit 4 (Day 1), Visit 9 (Day 32), and Visit 12 (Day 60). [REDACTED]

On Visit 2 (Day -14) subjects will attend the clinical unit for a short visit. At this visit they will be given advice on diet and exercise (in accordance with local practices) and training in SC injection administration, and fitted with a CGM sensor that the subject will be expected to wear continuously for the duration of the study until the second follow-up visit (Visit 11). [REDACTED]

[REDACTED]. On Visit 3 (Day -5), subjects will attend the clinical unit for a long visit and will undergo safety assessments and a mixed-meal tolerance test (MMTT). At this time, an ambulatory blood pressure monitoring (ABPM) device will be fitted on the contralateral arm to the CGM sensor and will be worn for 24 hours. [REDACTED]

[REDACTED] Subjects will be randomised on Visit 4 (Day 1) to receive either MEDI0382 or placebo and dosing will commence following predose baseline vital signs, blood tests (including HbA1c), an ECG, body weight measurement, [REDACTED]. Subjects will then return for daily dosing or remain overnight locally until Day 5, and thereafter will have visits at weekly intervals until a maintenance dose of [REDACTED] is established. At Visits 6, 7, and 8, ABPM recordings [REDACTED]. On the last day of dosing (Visit 9; Day 32), subjects will attend for a long day visit and undergo a repeat MMTT, HbA1c, ABPM, [REDACTED] and serial PK

sampling, alongside safety assessments. On the following day (first follow-up visit, Visit 10; Day 33) subjects will return to the clinic for a blood draw, urine collection, weight measurement, [REDACTED].

Two additional follow-up visits (Visit 11; Day 40±5 and Visit 12; Day 60±5) will be performed after the last dose for safety assessments.

[REDACTED]

[REDACTED]

[REDACTED]

3.1.2 Treatment Regimen

MEDI0382 or placebo will be administered once daily in the morning via SC injection:

- [REDACTED]
- [REDACTED]

[REDACTED]

3.1.4 Management of Study Medication Related Toxicities and Dose Modification

Nausea and Vomiting

If a subject experiences nausea and vomiting in relation to investigational product, in the first instance, conservative measures should be advised including reducing meal size and maintaining adequate hydration. Where necessary, if there is persistent vomiting a subject may be given an antiemetic to control his/her symptoms; a 5HT3 receptor antagonist (eg, ondansetron) or cyclizine is preferable in this situation, rather than antiemetics which may affect gastric emptying, and in particular dopamine receptor antagonists (eg, metoclopramide or domperidone).

[REDACTED]

[REDACTED]

[REDACTED]	[REDACTED]	[REDACTED]
[REDACTED]	[REDACTED]	[REDACTED]
[REDACTED]	[REDACTED]	[REDACTED]

[REDACTED]

[REDACTED]	[REDACTED]	[REDACTED]
[REDACTED]	[REDACTED]	[REDACTED]
[REDACTED]	[REDACTED]	[REDACTED]

[REDACTED]

[REDACTED]

[REDACTED]	[REDACTED]	[REDACTED]	[REDACTED]
[REDACTED]	[REDACTED]	[REDACTED]	[REDACTED]
[REDACTED]	[REDACTED]	[REDACTED]	[REDACTED]
[REDACTED]	[REDACTED]	[REDACTED]	[REDACTED]

[REDACTED]

[REDACTED]

[REDACTED]

Management of Hyperglycaemia and Rescue Therapy

In subjects who have sustained hyperglycaemia [REDACTED] additional open-label rescue therapy should be considered by the investigator and should be documented in the relevant section of the CRF. For subjects where hyperglycaemia

is suspected, additional venous fasting plasma glucose measurements may be performed if necessary to investigate further.

Rescue therapy should be considered by the investigator following discussion with the medical monitor if any of the following apply:

- Fasting plasma glucose >200 mg/dL (11.1 mmol/L) on two occasions less than 8 days apart
- Three capillary plasma glucose levels > 250 mg/dL (13.9 mmol/L) in one week
- More than 30% of readings in hyperglycaemic range on CGM defined as > 250 mg/dL (13.9 mmol/L) in one week

If rescue medication is required, subjects should continue to participate in the study and receive their study medication. An interim prescription of the rescue medication will be provided by the study site if necessary, but continued prescription of rescue therapy will remain the responsibility of the primary care physician or usual diabetes physician. Rescue medication will not be provided by the Sponsor for this study.

Investigators should consider discontinuing the investigational product in subjects with persistent fasting venous plasma glucose level of > 260 mg/dL (14.4 mmol/L), despite a maximum tolerated dose (MTD) of rescue therapy to enable optimization of the subject's glycaemic control. The subject should however remain in the study for all other study procedures and continued follow-up until their scheduled end of study date.

[Redacted]	[Redacted]
[Redacted]	[Redacted]
[Redacted]	[Redacted]
[Redacted]	[Redacted]
[Redacted]	[Redacted]
[Redacted]	[Redacted]

[REDACTED]

[REDACTED]

[REDACTED]

[REDACTED]

[REDACTED]

[REDACTED]

[REDACTED]

Management of Hypoglycaemia

A hypoglycaemic event is considered severe if associated with severe cognitive impairment requiring external assistance for recovery, as defined by the American Diabetes Association; clinically significant hypoglycaemia is defined as a capillary or venous plasma glucose reading of < 3.0 mmol/L (54 mg/dL). Spontaneous and clinically significant hypoglycaemia has not been experienced in prior studies with MEDI0382 up to a dose of [REDACTED] alongside metformin treatment.

All subjects will be provided with a diary and a glucose meter and will be advised to check their capillary plasma glucose level if they have symptoms of hypoglycaemia (hunger, dizziness, shaking, sweating, or irritability) or feel unwell and will be expected to record the level in their diary. Local protocols for treatment and follow-up of any hypoglycaemic episode should be followed. Any clinically significant hypoglycaemia should be reported by investigators as an AE regardless of whether or not the subject is experiencing symptoms or not. Pharmacological treatments administered for hypoglycaemia, eg, dextrose/glucose tablets, glucagon etc should be recorded in the electronic case report form (eCRF) as concomitant medications.

For subjects who experience a severe hypoglycaemic episode or a clinically significant episode of hypoglycaemia (defined as a capillary or venous plasma glucose reading of < 54 mg/dL (3.0 mmol/L) or an interstitial glucose reading < 54 mg/dL (3.0 mmol/L) recorded on CGM on two occasions across 15 minutes) a reduction in total daily dose of insulin of 20% should be made from the time of awareness of the event. If the subject is not using insulin during the study, a 50% dose reduction in oral medication should be made in the following order of preference: sulfonylureas, glitinide, pioglitazone, metformin, DPPIV inhibitors. Dose reduction should also be considered at the discretion of the investigator and following discussion with the medical monitor if > 2% of interstitial glucose readings on CGM are < 70 mg/dL (3.9 mmol/L).

Decline in Renal Function

For subjects who have a eGFR of 30-44 mL/min/1.73 m² (inclusive) at screening and are taking an existing dose of metformin that is higher than the recommended dose for that degree

of renal impairment, the dose of metformin should be reduced or discontinued at Visit 2 in accordance with local guidelines on metformin prescription in renal impairment, or to 500 mg once daily if no guidance is in place. Similarly, any subject experiencing a decline in eGFR during the study to 30-44 mL/min/1.73 m² (inclusive) should have their dose of metformin reduced or discontinued as described above.

For subjects who are found to have a decline in renal function to eGFR < 30 mL/min/1.73 m² during the study, the subject should also be advised to stop metformin therapy and any other medications that are contraindicated for this degree of renal impairment.

For subjects who are eligible to take part in the study and are taking other medications for diabetes that are prescribed at a higher dose than recommended for their degree of renal insufficiency, dose reduction should be performed at Visit 2 in accordance with local treatment guidelines or the drug labelling.

For subjects who are found to have a decline in renal function to eGFR ≤ 25 mL/min/1.73 m² during the study, the subject should undergo a repeat eGFR level one week later, and if the eGFR remains ≤ 25 mL/min/1.73 m² on a second consecutive test, the investigational product (IP) should be discontinued, and the subject should also be advised to stop metformin therapy (if they have not already done so) and any other medications that are contraindicated for this degree of renal impairment. However, the subject should remain in the study for all other study procedures until their scheduled end of study.

3.2 Rationale for Dose, Population, and Endpoints

3.2.1 Dose Rationale

[REDACTED]

[REDACTED]

[REDACTED]

[REDACTED]

[REDACTED]

[REDACTED]

[REDACTED]

[REDACTED]	[REDACTED]	[REDACTED]	[REDACTED]	[REDACTED]
[REDACTED]	[REDACTED]	[REDACTED]	[REDACTED]	[REDACTED]
[REDACTED]	[REDACTED]	[REDACTED]	[REDACTED]	[REDACTED]
[REDACTED]	[REDACTED]	[REDACTED]	[REDACTED]	[REDACTED]
[REDACTED]	[REDACTED]	[REDACTED]	[REDACTED]	[REDACTED]

[REDACTED]

3.2.2 Rationale for Study Population

MEDI0382 is a GLP-1 and glucagon receptor co-agonist that promotes glucose lowering and weight loss and is targeted at subjects with T2DM. Renal impairment attributed to diabetic kidney disease is common in patients with longstanding T2DM. The entry criteria with respect to T2DM and eGFR of ≥ 30 and < 60 mL/min/1.73 m² both maximise recruitment potential and provide efficacy, safety, and tolerability data in the intended clinical population who concurrently have moderate renal impairment. The eligibility criteria also permit inclusion of subjects with an HbA1c of 6.5-10.5% and those who are treated with any combination of oral therapy and/or insulin, which reflects the natural history of late stage T2DM and concurrent chronic kidney disease (CKD). There is no requirement for a given number of subjects in each gender to be enrolled. It is intended that at least 50% (n=20) of subjects enrolled in the study will be taking insulin at a dose of ≥ 20 units/day to enable any effect of MEDI0382 on insulin dose adjustment to be observed. In addition, it is intended that approximately 40% (n=16) of subjects enrolled in the study will have an eGFR of ≥ 30 and < 45 mL/min/1.73 m² and at least 40% (n=16) of subjects enrolled in the study will have an eGFR of ≥ 45 and < 60 mL/min/1.73 m². This is to ensure subjects at both ends of the moderate renal impairment spectrum are adequately represented.

3.2.3 Rationale for Endpoints

Primary Endpoint

The primary endpoint of glucose AUC as measured by MMTT is required to evaluate the efficacy of the [REDACTED] dose of MEDI0382 in this population of subjects with T2DM and renal impairment.

Secondary Endpoints

Safety and Tolerability

[REDACTED]

[REDACTED]

Additional Measures of Glucose Lowering and Weight Loss

To better characterise the glucose-lowering efficacy of MEDI0382 across 32 days of dosing in renally impaired subjects, additional markers of glucose control including HbA1c and fasting glucose level will be measured, alongside measures of the percentage of time spent within a target glucose range measured by CGM. [REDACTED]

[REDACTED]

Pharmacokinetic Profile and Immunogenicity

Plasma concentrations of MEDI0382 at the [REDACTED] dose level will be used to evaluate the PK profile (C_{max} , time to maximum concentration [T_{max}], AUC_{tau}) in this specific population. In addition, C_{trough} at each dose level will be evaluated to ensure exposure to the drug.

Prior studies of MEDI0382 and metformin co-therapy have shown no signs of a PK interaction between MEDI0382 and metformin. Plasma samples predose (C_{trough}) will be collected and stored for analysis of metformin levels in case that renal function data warrant such analyses.

Anti-drug antibodies (ADA) incidence rate and titre will be tabulated for each treatment to monitor immunogenicity. Tiered analyses will be performed to include screening, confirmatory and titre assay components; samples confirmed positive for ADA will be tested

and analysed for antibody titre and reported, and may be utilised for further characterisation of the ADA response.

4 MATERIALS AND METHODS

4.1 Subjects

4.1.1 Number of Subjects

It is planned to randomise approximately 40 subjects across multiple study sites.

4.1.2 Inclusion Criteria

Subjects must meet all of the following criteria:

- 1 Age ≥ 18 and < 85 years at screening.
- 2 Signed and dated written informed consent (with the exception of consent for genetic and nongenetic research) prior to performing any protocol-related procedures, including screening evaluations.
- 3 Diagnosed with T2DM with glucose control managed with any insulin*¹ and/or oral therapy combination where no significant dose changes of oral therapy of more than 50% have occurred in the 3 months prior to screening
- 4 Body mass index (BMI) between 25 and 45 kg/m² (inclusive) at screening
- 5 HbA1c range of 6.5 % to 10.5% (inclusive) at screening
- 6 Renal impairment with eGFR ≥ 30 and < 60 mL/min/1.73 m² at screening. Approximately 16 subjects (40%) are required to have a screening eGFR ≥ 30 and < 45 mL/min/1.73 m² and at least 16 subjects (40%) are required to have screening eGFR ≥ 45 and < 60 mL/min/1.73 m². eGFR will be determined by the chronic kidney disease-epidemiology collaboration (CKD-EPI) equation. In instances where the eGFR estimated during the screening period is outside the range expected from the subject's medical history, the subject may be re-tested once.
- 7 Females of childbearing potential must have a negative pregnancy test at screening and randomisation, and must not be lactating. Women of childbearing potential who are sexually active with a nonsterilized male partner must be using at least one highly effective method of contraception (see Section 10.2 for definition of females of childbearing potential and for a description of highly effective methods of contraception) from screening and up to 4 weeks after the last dose of investigational product. It is strongly recommended for the male partner of a female subject to also use male condom plus spermicide throughout this period. Cessation of contraception after this point should be discussed with a responsible physician. Periodic abstinence, the rhythm method, and the withdrawal method are not acceptable methods of contraception.

*¹ At least 50% of subjects (n=20) enrolled in the study should be taking insulin at a total daily dose of ≥ 20 units.

4.1.3 Exclusion Criteria

Any of the following would exclude the subject from participation in the study:

- 1 History or presence of significant medical or psychological conditions, including substance dependence/abuse, or significant abnormalities in laboratory parameters or vital signs including ECG, which in the opinion of the investigator, would compromise the subject's safety or successful participation in the study. As an example, severe anaemia (haemoglobin < 7.0 g/dL) could be exclusionary due to blood sampling required by the protocol, at the discretion of investigator.
- 2 Concurrent participation in another interventional study of any kind and repeat randomisation in this study is prohibited
- 3 Any subject who has received another investigational product as part of a clinical study or a GLP-1 analogue-containing preparation within the last 30 days or 5 half-lives of the drug (if known; whichever is longer) at the time of Visit 2
- 4 Any subject who has received any of the following medications within the specified timeframe prior to the start of the study (Visit 2) (see Section 4.7.2 for further details)
 - Herbal preparations within 1 week prior to the start of dosing (Visit 4) or drugs licensed for control of body weight or appetite (eg, orlistat, bupropion-naltrexone, phentermine-topiramate, phentermine, lorcaserin) within 30 days (or 5 half-lives of the drug) prior to the start of dosing (Visit 4)
 - Aspirin (acetylsalicylic acid) at a dose greater than 150 mg once daily and within the last 3 days prior to the start of the run-in period (Visit 2)
 - Paracetamol (acetaminophen) or paracetamol-containing preparations at a total daily dose of greater than 3000 mg and within the last 3 days prior to the start of the run-in period (Visit 2)
 - Ascorbic acid (vitamin C) supplements at a total daily dose of greater than 1000 mg and within the last 3 days prior to the start of the run-in period (Visit 2)
 - Opiates, domperidone, metoclopramide, or other drugs known to alter gastric emptying and within 2 weeks prior to the start of dosing (Visit 4)
- 5 Severe allergy/hypersensitivity to any of the proposed study treatments or excipients
- 6 Symptoms of acutely decompensated blood glucose control (eg, thirst, polyuria, weight loss), a history of type 1 diabetes mellitus or diabetic ketoacidosis
- 7 Subjects who have undergone a renal transplant

- 8 Subjects with suspicion of acute or subacute renal function deterioration (eg, subjects with large fluctuations of creatinine values documented within the 6 months prior to screening)
- 9 Significant inflammatory bowel disease, gastroparesis, or other severe disease or surgery affecting the upper GI tract (including weight-reducing surgery and procedures) which may affect gastric emptying or could affect the interpretation of safety and tolerability data
- 10 History of acute or chronic pancreatitis
- 11 Significant hepatic disease (except for non-alcoholic steatohepatitis or nonalcoholic fatty liver disease without portal hypertension or cirrhosis) and/or subjects with any of the following results:
 - Aspartate transaminase (AST) $\geq 3 \times$ upper limit of normal (ULN)
 - Alanine transaminase (ALT) $\geq 3 \times$ ULN
 - Total bilirubin $\geq 2 \times$ ULN
- 12 Poorly controlled hypertension defined as:
 - Systolic BP > 180 mm Hg
 - Diastolic BP ≥ 100 mm Hg

after 10 minutes of seated rest and confirmed by repeated measurement at screening. Subjects who fail BP screening criteria may be considered for 24-hour ABPM at the discretion of the investigator. Subjects who maintain a mean 24-hour systolic BP ≤ 180 or diastolic BP < 100 mm Hg with a preserved nocturnal dip of $> 15\%$ will be considered eligible

- 13 Unstable angina pectoris, myocardial infarction, transient ischemic attack or stroke within 3 months prior to screening, or subjects who have undergone percutaneous coronary intervention or a coronary artery bypass graft within the past 6 months or who are due to undergo these procedures at the time of screening
- 14 Severe congestive heart failure (New York Heart Association Class III or IV)
- 15 Basal calcitonin level > 50 ng/L at screening or history/family history of medullary thyroid carcinoma or multiple endocrine neoplasia
- 16 History of neoplastic disease within 5 years prior to screening, except for adequately treated basal cell skin cancer, squamous cell skin cancer, or in situ cervical cancer
- 17 Any positive results for serum hepatitis B surface antigen (HBsAg), hepatitis C antibody, and human immunodeficiency virus (HIV) antibody
- 18 Nephrotic range proteinuria defined as spot urine ACR > 250 mg/mmol at screening
- 19 History of substance dependence, alcohol abuse, or excessive alcohol intake (defined as an average weekly intake of > 21 alcoholic drinks for men or > 10 alcoholic drinks for women) within 3 years prior to screening, and/or a positive screen for drugs of abuse or alcohol at screening or on Day -5. Subjects who use tricyclic antidepressants or

benzodiazepines for an established clinical indication may be permitted to enter the study based upon the judgement of the investigator.

- 20 Involvement of any AstraZeneca, MedImmune, contract research organization, or study site employee or their close relatives

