This is a randomised, double-blind, placebo-controlled study to evaluate the safety, tolerability, efficacy, and PK profile of MEDI0382 titrated from [REDACTED] up to [REDACTED] and administered once daily by subcutaneous (SC) injection over 32 days in subjects with T2DM and renal impairment (eGFR ≥ 30 and < 60 mL/min/1.73 m²). The study has a 14-day run-in period of diet and exercise and continuous glucose monitoring (CGM), a 32-day treatment period, and a 28-day follow-up period. Diet and exercise guidance will be according to local practices. It is planned to randomise approximately 40 subjects across multiple study sites. Subjects will be consented, screened for suitability, and randomised within 40 days of screening, if eligible.

Throughout the study, subjects will have the choice to either travel to the clinic for visits or stay overnight locally whenever consecutive daily visits are required. Subjects will be expected to fast for at least 8 hours overnight prior to Visit 3 (Day -5), Visit 4 (Day 1), Visit 9 (Day 32), and Visit 12 (Day 60).

On Visit 2 (Day -14) subjects will attend the clinical unit for a short visit. At this visit they will be given advice on diet and exercise (in accordance with local practices) and training in SC injection administration, and fitted with a CGM sensor that the subject will be expected to wear continuously for the duration of the study until the second follow-up visit (Visit 11).

On Visit 3 (Day -5), subjects will attend the clinical unit for a long visit and will undergo safety assessments and a mixed-meal tolerance test (MMTT). At this time, an ambulatory blood pressure monitoring (ABPM) device will be fitted on the contralateral arm to the CGM sensor and will be worn for 24 hours.

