4.1.4 Subject Enrollment and Randomisation

Study participation begins (ie, a subject is “enrolled”) once written informed consent is obtained. Once informed consent is obtained, a subject identification (SID) number will be assigned by a central system (eg, an interactive voice/web response system, [IXRS]) and the screening evaluations may begin to assess study eligibility (inclusion/exclusion) criteria. The SID number will be used to identify the subject during the screening process and throughout study participation, if applicable.

Approximately 40% of subjects (n = 16) enrolled in the study will have an eGFR of ≥ 30 and < 45 mL/min/1.73 m² and at least 40% (n = 16) will have an eGFR of ≥ 45 and < 60 mL/min/1.73 m². In addition, at least 50% of subjects (n=20) enrolled in the study should be taking insulin at a total daily dose of ≥ 20 units.

A master log of all consented subjects will be maintained at the site and will document all screening failures (ie, subjects who are consented but do not meet study eligibility criteria and/or are not randomised), including the reason(s) for screening failure.

Subjects who fail to meet the inclusion/exclusion criteria (ie, screening failures) should not, under any circumstances, be randomised or receive investigational product. There can be no exceptions to this rule. Subjects who are enrolled, but subsequently found not to meet all the eligibility criteria, should not be randomised or initiated on treatment. If randomisation and treatment initiation occur for a subject found not to meet any eligibility criterion, withdrawal of the subject from the study will be the decision of the medical monitor.

Subjects may be rescreened once if, in the opinion of the investigator, there is a reason to believe they may be eligible.

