- e Vital Signs Schedule (blood pressures, pulse rate, respiratory rate, and temperature): on days where ABPM is due to be checked a set of vital signs should be performed prior to application of the ABPM cuff. Blood pressure should be measured at heart level and opposite to the arm where the CGM device is applied, with the subject supine and rested for 10 minutes prior to the measurement. For time points where ECG recording precedes vital sign measurement, the 10-minute rest in the supine position prior to the ECG suffices for the rest prior to vital sign measurement.
- f Following a minimum 8-hour fast overnight, a blood sample for glucose will be taken immediately (within 15 minutes) prior to the subject drinking one entire can of Ensure Plus as a standardised meal (ie, '0 minutes'). Blood samples for glucose will additionally be drawn at 15, 30, 45, 60, 90, 120, 180 and 240 minutes (\pm 5 minutes) after consumption of the standardised meal.
- g Urine sample for urine albumin/creatinine ratio at Visit 1 screening may be taken at any time and does not need to be a first void specimen. At Visit 2 (Day-14) and Visit 3 (Day -5) urine sample for urine albumin / creatinine ratio should be taken as an early morning specimen during the first void of the day.
- h Pregnancy tests do not need to be conducted in women who are surgically sterile (ie, bilateral tubal ligation, bilateral oophorectomy, or complete hysterectomy) or are post-menopausal (defined as at least 1 year since last menses and/or having an elevated follicle stimulating hormone laboratory value which is in the post-menopausal range in previous laboratory test results).
- i CGM device should be worn continuously throughout the study until V11 and the sensor should be applied to the arm, taking into account subject preference and which side the ABPM device will be used. The sensor applied to the skin is single use and may not be re-attached once removed.
- j Subjects will be fitted with the ABPM device whilst at the clinical unit, which may involve practice inflations. The ABPM device should be applied on the arm contralateral to the arm where the CGM device is applied. The subject will then wear the monitor / cuff for approximately 24 hours and will remove at the end of the 24-hour period whilst at home and will return the monitor at their next visit.
- k [REDACTED]

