7.4 Changes to the Protocol and Informed Consent Form

Study procedures will not be changed without the mutual agreement of the Principal Investigator and MedImmune.

Substantial changes must be documented in a study protocol amendment. MedImmune will distribute amended versions of the protocol to the principal investigator(s). Before implementation, amended protocols must be approved by relevant IRB/IEC (see Section 7.2)

and according to local requirements, the national regulatory authority approval. The IRB/IEC must also approve revisions to the informed consent form, advertising, and any other written information and/or materials resulting from the change to the protocol.

If local regulations require, any unsubstantial changes will be communicated to or approved by each IRB/IEC.

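### Exclusion criterion 12 readmits subjects on 24-hour blood pressure with *or* where *and* is needed, so a mean of 200/95 or 170/110 meets the blood pressure part

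*Protocol*

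**What the plan says.** Criterion 12 in Protocol Section 4.1.3 defines poorly controlled hypertension by two bullets: systolic above 180 mm Hg, and diastolic at or above 100 mm Hg. Both are seated readings, confirmed by repeat measurement at screening. No *and* or *or* joins the bullets.

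A route back in follows: "Subjects who fail BP screening criteria may be considered for 24-hour ABPM at the discretion of the investigator". The test for re-entry is "Subjects who maintain a mean 24-hour systolic BP ≤ 180 or diastolic BP < 100 mm Hg", plus a nocturnal dip above 15%.

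Criterion 11, directly above, does say how its bulleted liver limits combine: "and/or subjects with any of the following results". Criterion 12 has no such phrase. Nothing else in the visible text of the protocol or SAP restates or corrects the blood pressure rule.

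Section 4.1.4 bars the randomisation of anyone who fails the eligibility criteria and adds: "There can be no exceptions to this rule".

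**The concern.** The re-entry limits mirror the exclusion limits exactly: at or below 180 against above 180, and below 100 against at or above 100. The sentence therefore reads as the negation of the two bullets. If either bullet is enough to exclude, its negation needs both limits to be met. Joining them with *or* lets a subject return while the 24-hour mean still breaches one limit, possibly the same one that caused the failure.

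At stake is a stated safety threshold at entry, in a trial where blood pressure is itself a secondary safety endpoint. Because eligibility is applied strictly, sites need one rule that gives one answer. The point does not touch the primary analysis, the sample size or the comparison between arms.

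**Working it through.** There is no planned figure to reproduce; this is a check of logic.

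**Inputs (Section 4.1.3, criterion 12)**
- Exclusion limits: systolic > 180; diastolic ≥ 100.
- Re-entry as written: 24-hour mean systolic ≤ 180 *or* diastolic < 100.
- Further conditions: the investigator chooses to offer monitoring, and the nocturnal dip exceeds 15%. The counts below set these aside because the documents give no frequency for either.

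**Step 1: individual values of the 24-hour mean**

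| Mean | Would either limit exclude? | Would exclusion need both? | Re-entry with *or* (as written) | Re-entry with *and* |
|---|---|---|---|---|
| 200/95 | excluded | not excluded | passes | refused |
| 170/110 | excluded | not excluded | passes | refused |
| 200/110 | excluded | excluded | refused | refused |
| 170/95 | not excluded | not excluded | passes | passes |

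Over an integer grid (systolic 100 to 240, diastolic 50 to 140, diastolic below systolic), the *and* rule is the exact complement of either-limit exclusion. The *or* rule is the exact complement only of an exclusion that needs both limits breached together.

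**Step 2: counting the logical cases under either-limit exclusion**

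A subject can fail screening in 3 ways: systolic only, diastolic only, or both. The 24-hour mean can be in 4 states: neither limit breached, systolic only, diastolic only, or both. That gives 3 × 4 = 12 combinations.

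- *Or*, taken literally, refuses only a mean that breaches both limits. It admits 3 × 3 = 9, of which 3 × 2 = 6 still breach one limit.
- *Or*, read as whichever limit was failed: a systolic-only failure admits 2 states, a diastolic-only failure admits 2, and a failure on both admits 1. The total is 2 + 2 + 1 = 5, of which 2 breach the other limit. For example, a subject who failed at 170/105 could enter with a mean of 185/95.
- *And* admits one state per type of failure, 3 × 1 = 3, and 0 still breach a limit.

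These are unweighted logical cases, not expected frequencies.

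**Step 3: the reading under which *or* is consistent**

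If exclusion needs both limits breached, only one type of failure exists. *Or* then admits 3 of the 4 mean states, none of which breaches both limits. The price is that a confirmed isolated 200/95 is never excluded by this criterion.

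**Step 4: which reading is the ordinary one**

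Three things favour either-limit exclusion. Criterion 11 states that rule for its own bullets. The two definitions of acute kidney injury in Section 4.1.6 also stand as bullets without a connector, and they are plainly alternatives. Lastly, a rule that leaves 200/95 outside poorly controlled hypertension is implausible for a safety exclusion.

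**The case against.** The strongest reply is that the text is ambiguous rather than wrong. The bullets carry no connector, and if both limits must be breached to exclude, *or* is the correct negation. It is true that the error depends on reading the bullets as alternatives. That reading is much the better supported, however, and the others do not rescue the sentence: one leaves isolated severe elevation unexcluded, and the other can admit a subject over the limit that was not originally failed.

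A second reply is that the consequence is small because other checks apply. This largely stands.
- Monitoring is offered only at the investigator's discretion.
- Criterion 1 separately allows exclusion for "significant abnormalities in laboratory parameters or vital signs including ECG, which in the opinion of the investigator" would put safety at risk, and meeting the re-entry sentence does not override it.
- Vital signs are taken at Day -5 and before dosing on Day 1.
- Every subject has 24-hour monitoring at Day -5 (Synopsis, Study Design): "an ambulatory blood pressure monitoring (ABPM) device will be fitted on the contralateral arm to the CGM sensor and will be worn for 24 hours".

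These are matters of judgement, whereas criterion 12 is there to fix a limit. The visible text does not make the Day -5 recording an eligibility gate. Table 9 says the subject "will return the monitor at their next visit", and the next clinic visit is Day 1, when randomisation and first dosing take place. The visible examples of reasons to stop treatment in Section 4.1.6 include no blood pressure threshold, although parts of Section 3.1.4 are redacted and may contain one.

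A third reply is that adding *or* between the bullets is only style if either-limit exclusion is clearly meant. That is fair: the change to *and* carries the substance, and the other edit removes the remaining doubt.

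**Conclusion.** The concern holds. On the ordinary reading that either limit excludes, the re-entry sentence is wrong as written; on the other readings the criterion is ambiguous or leaves a gap. A 24-hour mean of 200/95 or 170/110 meets the blood pressure part of re-entry, subject to the dip condition and to the investigator having offered monitoring.

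The point is minor. The documents give no basis for estimating how many subjects are affected. None or very few is likely, and each would be 1/40 = 2.5% of the planned sample. Confidence is moderate because the conclusion rests on the either-limit reading, which the text implies but does not state.

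**What to change.** Confirm that either limit is meant to exclude. Then make two one-word edits to criterion 12: insert *or* between the systolic and diastolic bullets, and replace *or* with *and* between the two limits in the re-entry sentence, leaving the dip condition as it is. Re-entry then requires a 24-hour mean within both limits.

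No analysis change follows. On process, Section 7.4 says: "Substantial changes must be documented in a study protocol amendment". It also requires ethics approval before an amended protocol is used. If the sponsor classes this edit as substantial, it is best carried with another amendment.

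The edits can only narrow eligibility, so a few more subjects may fail screening. Section 9.1 records that recruitment was already short in the eGFR 30 to 45 group. That cost falls only on subjects whose blood pressure is still over a limit the protocol itself sets.
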